4.2.4.3 Sensitivity and supplementary analyses for primary endpoint

To further support the primary endpoint analysis and to examine the influence of missing data due to drop-out and/or receiving rescue therapy, sensitivity and supplementary estimands described in Section 4.2.4.1 are defined and will be addressed using an MMRM analysis at Week 28.

An imputation sensitivity analysis will test the assumption of MAR that is made by the MMRM analysis. For this purpose, a model that assumes missing not at random (MNAR) will be used, whereby assumptions for the missing data “stress test” the MAR assumptions of the primary analysis, by positing outcomes that, while clinically plausible, are likely to be worse for the Total EBID group than the outcomes assumed by MAR. A plausible stress test could assume that the outcome for the Total EBID treatment is somewhat worse than would be predicted by MMRM from the study data. Such a stress test would appropriately disadvantage the estimate of treatment effect, compared to the estimate of the primary analysis. In this way the MAR assumption of the primary analysis could be stress tested.

If this is so, the proposed MNAR sensitivity analysis, which assumes that the trajectory of withdrawals from the Total EBID group, regardless of reason for withdrawal, is as bad as that of PBO patients, is quite conservative and a reasonable stress test of the already somewhat conservative MAR assumption of a common trajectory for withdrawals. Note that this approach constitutes a pattern mixture model (Molenberghs and Kenward 2007). The patterns here are

defined by the time of withdrawal combined with the treatment group. The time of withdrawal is used in the definition of the pattern to allow the estimate to take account of the improvement over time that tends to be observed in all patients. By the end of the study earlier withdrawals are likely to have improved somewhat more from their last observation, than late withdrawals. Specifically, for patients who drop out after visit t , the change from baseline at visit $t + n$ will be assumed to be the mean for visit t plus the difference in the means of the PBO group at visits t and $t + n$, given the study data. Then, the overall estimate of treatment effect is obtained by averaging the estimates across the dropout patterns, according to the proportions of dropouts occurring at each visit. Note that in this analysis, PBO missing observations are imputed assuming MAR and follow the pattern of observed PBO observations, and missings for the Total EBID group are assumed MNAR.

In summary, the pattern mixture models will be implemented by multiple imputation via the following steps;

Step 1: Non-monotone missing data (usually relatively infrequent) will be imputed using the MCMC option of SAS PROC MI with treatment, baseline HbA1c, background diabetes therapy strata (drug naïve, metformin only, SU only, and metformin +SU) and value of the endpoint at each visit. This will create a monotone missing pattern in the dataset within each treatment group. This step will create 1000 imputed datasets.

Step 2: The values for each pattern will be imputed via the chained equation method, using SAS PROC MI option MONOTONE REG (). The MNAR imputation is achieved by using only appropriate study data for each pattern. For example, to impute for time t if the EBID missing data has the trajectory of PBO, include only PBO observations up to and including time t , plus only observations from patients in the EBID group that have observations up to but not beyond time $t-1$. First, all missings for the first post-baseline visit are imputed, then missings for the next visit are imputed using observed data plus the missings just imputed; and so on to the final visit. The covariates used in the model will be baseline HbA1c, background diabetes therapy strata (drug naïve, metformin only, SU only, and metformin +SU) and HbA1c measured at time $t-1$.

Step 3: The imputed data from Step 1 and Step 2, along with observed data will be analyzed using an MMRM model for the outcome of change from baseline with treatment, baseline HbA1c, background diabetes therapy strata (drug naïve, metformin only, SU only, and metformin +SU), week of visit, baseline HbA1c-by-week interaction and treatment-by-week interaction as the fixed effects. The variance - covariance structure to be used for this modelling will be unstructured (UN). The estimates from multiple imputed datasets will be combined using Rubin's combination rules for statistical inference (Rubin, 1987) using PROC MI ANALYZE.

The seed used will be 88281 for both steps 1 and 2.

At Step 1, if a categorical covariate has more than 2 levels, then dummy coding has to be performed to present it as either 0/1 or 1/2. If categorical variable has X categories ($X > 2$) then we would create $X-1$ dummy variables, using the rule described in the table below.

Table 4 Dummy variables

Category	Dummy variable 1	Dummy variable 2	...	Dummy variable X-1
A	1	0		0
B	0	1		0
...	0	0		0
X-1	0	0		1
X	0	0		0

A supplemental to the primary analysis and a sensitivity to the supplemental of the primary analysis will also be performed. In these analyses, data after rescue medication use or date of IP discontinuation will be included in the MMRM analysis and MI pattern mixture modelling.

Further sensitivity analysis will be as described in section 4.2.4.2, where it will compare active treatment group doses vs Placebo (EBID vs. PBO).

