#### 7.4. Discontinuations

The criteria for enrollment must be followed explicitly. If a patient who does not meet enrollment criteria is inadvertently enrolled, that patient will continue in the study unless, in the opinion of the Sponsor's physician responsible for the study, the patient should be discontinued for safety reasons. The Sponsor or its designees must be contacted.

In addition, patients will be discontinued from the treatment period of the study in any of the following circumstances:

- if the patient experiences a loss of glycemic control, as evidenced by:
  - increase in absolute HbA1c  $\geq 0.5\%$  from baseline at 2 consecutive scheduled visits which are at least 1 month apart, prior to study completion
  - fasting blood glucose  $>250$  mg/dL (13.9 mmol/L) or non-fasting glucose  $>300$  mg/dL (16.7 mmol/L) for 4 days in a 7-day period as measured by SMBG. The patient will return to the clinic for a confirmatory fasting glucose, if possible, or a non-fasting glucose. If by local laboratory measurement a fasting glucose is  $>250$  mg/dL (13.9 mmol/L) or a non-fasting glucose is  $>300$  mg/dL (16.7 mmol/L), the patient will be discontinued from the study
- if a female patient becomes pregnant
- if the patient misses more than 10 consecutive days of study therapy
- if the patient misses more than 10 consecutive days of oral antidiabetes therapy
- if metformin or an SU is added or altered for more than 10 consecutive days or 10 days in a 30-day period after study entry
- if a patient uses excluded concomitant medications ([Section 7.2](#), Exclusion Criteria)

- if the investigator decides that the patient should be withdrawn. If this decision is made because of a serious adverse event or a clinically significant laboratory value, the study drug is to be discontinued and appropriate measures are to be taken. The Sponsor or its designee is to be notified immediately
- if the patient or attending physician requests that the patient is withdrawn from the study
- if the investigator or the Sponsor, for any reason, stops the study or stops the patient's participation in the study.

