4.1.3 Handling of missing data

4.1.3.1 Missing efficacy data

Missing data in this study may result from patients discontinuing from the study prematurely or missing intermediate visits or selected assessments while remaining on study. Every effort will be made to obtain the CSP-required data for all study assessments that are scheduled for all patients who have been enrolled. Data collected after initiation of rescue therapy will be excluded from most efficacy analyses (see Section 4.2.4 for details) and therefore these data will effectively be handled as missing in analyses. For efficacy analyses, in general missing observations will not be imputed, except those inherited from the mixed model repeated measures (MMRM) which implicitly assumes that data are missing at random (MAR).

Sensitivity of the primary analysis will be performed using pattern mixture model imputation for missing values and details of this imputation is provided in Section 4.2.4.3.

Missing at Random (MAR) refers to missingness that is independent of missing responses, conditionally on observed responses and covariates. As the imputation strategy should always consider the dropout patterns and the time-course of the efficacy measurements by treatment, the pre- and post- withdrawal values will be assessed to understand the impact of dropouts on the efficacy results. The primary efficacy endpoint of HbA1c data will be visually examined to explore the missingness patterns by (1) plotting each individual patient's HbA1c change trajectory in completers, side-by-side with those from the early study drug withdrawal, and by (2) plotting the early study drug withdrawal's last HbA1c change data, overlaid with the box plot by visit from completer population.

For categorical endpoints HbA1c goals of <6.5%, ≤6.5% and <7% at 28 weeks, any patient with missing HbA1c value at 28 weeks will be considered as failed to meet HbA1c <6%, ≤6.5% and <7%, respectively, at endpoint (28 Weeks).

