4.2.4.2 Analysis of primary variable

The MMRM analysis of the primary endpoint in the Evaluable analysis set will be considered the primary analysis.

The primary efficacy analysis will compare treatment groups (Total EBID vs. PBO) with respect to change in HbA1c from baseline Visit 3 (Week 0) to Visit 11 (Week 28) using the MMRM approach. The model will include change in HbA1c as the dependent variable and treatment, baseline HbA1c, background diabetes therapy strata (drug naïve, metformin only, SU only, and metformin + SU), week of visit, baseline HbA1c-by-week interaction and treatment-by-week interaction as the fixed effects. The variance - covariance structure to be used for this modelling will be unstructured (UN); if the model does not converge with unstructured variance – covariance matrix, then autoregressive order 1 (AR [1]) and heterogeneous autoregressive order 1 (ARH [1]) structures will be tried and the covariance structure will be decided based on model convergence status and the Akaike information criterion. The restricted maximum likelihood (REML) method will be used for parameter estimation. The least squares (LS) mean, 2-sided 95% confidence interval, and p-value of the difference in the change of HbA1c between the Total EBID and PBO groups at Visit 11 (Week 28) will be provided. The mean (SD) observed HbA1c at baseline and Week 28 will also be given by treatment group.

HbA1c data from post-baseline visits (including ED) will potentially be included in the MMRM analysis. In addition, if a patient’s last available measurement during the 28-week assessment period is from an unscheduled visit or ED visit, the value will be programmatically mapped to the next closest scheduled visit and potentially included in the MMRM analysis. See Section 4.1.3 for details on missing data handling and Section 4.2.4.1 for details on handling of data after IEs.

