The effects of the study medications on HOMA will be examined. The pancreatic beta-cell function (HOMA-B) and peripheral and hepatic insulin sensitivity (HOMA-S) will be computed from a computerized HOMA model, the HOMA Calculator (Matthews et al 1985). The HOMA Calculator, developed by Diabetes Trials Unit at the Oxford Center for Diabetes, Endocrinology, and Metabolism, is a computer algorithm that takes account of variations in hepatic and peripheral glucose resistance, increases in the insulin secretion curve for plasma glucose concentrations above 10 mmol/L (180 mg/dL), and the contribution of circulating proinsulin (e.g., C-peptide) to estimate the steady state beta-cell function and insulin sensitivity, as percentages of a normal reference population. The model assumes %HOMA-B and %HOMA-S values of 100% in normal young adults as a recalibration.

HOMA parameters will be log transformed (natural logarithmic transformation). The observed values and change from baseline for these parameters will be summarized by visit using descriptive statistics (n, geometric mean, geometric coefficient of variation: GCV%, geometric standard deviation factor: GSD, arithmetic mean, standard deviation, coefficient of variation: CV%, median, minimum and maximum value) for the Full analysis set.

The same multiple imputation ANCOVA approach (as used for the analysis of FSG and FSI) will be used to analyze change from baseline Visit 3 (Week 0) to Visit 11 (Week 28) for HOMA-B and HOMA-S.

All HOMA parameters will be analyzed on a logarithmic scale (natural logarithmic transformation), and then back-transformed to the original scale for result presentation using the following formulae:

$$\text{Geometric Mean} = \exp(\text{mean}(\log(X)))$$

$$\text{SE of Geometric Mean} = \text{Geometric Mean} * \text{SE of Mean}(\log(X))$$

LS means will be back-transformed in the same way.

Separate tables of back-transformed and non-transformed results will be provided.

Homeostasis results will be listed.

Proportions of patients discontinuing the study due to failure to maintain glycemic control at Visit 11 (Week 28), and at each intermediate visit

Patients should be discontinued from the study if the patient experiences a loss of glycemic control, as evidenced by:

- Increase in absolute HbA1c $\geq 0.5\%$ from baseline at 2 consecutive scheduled visits which are at least 1 month apart, prior to study completion and/or

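### Step 2 of the pattern-mixture imputation uses only the preceding HbA1c value, so unless HbA1c is first-order Markov it does not deliver the MAR prediction claimed for placebo, and the sensitivity effect moves towards zero

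*SAP*

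**What the plan says.** SAP 4.2.4.3 tests the MAR assumption of the primary MMRM by giving exenatide withdrawals a placebo-like trajectory. For placebo it makes no departure from MAR: "PBO missing observations are imputed assuming MAR and follow the pattern of observed PBO observations". SAP 4.1.3.1 defines the term: "Missing at Random (MAR) refers to missingness that is independent of missing responses, conditionally on observed responses and covariates".

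Step 1, which fills intermittent gaps, uses treatment, baseline, strata "and value of the endpoint at each visit". Step 2, which fills the values after withdrawal, uses baseline, strata and a single lag: "and metformin +SU) and HbA1c measured at time $t-1". No reason is given for the narrower set. The FSG/FSI imputation in SAP 4.2.4.4 lists the endpoint at each visit in both of its steps.

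The primary MMRM (SAP 4.2.4.2) has an unstructured covariance. Only if that fails to converge, "then autoregressive order 1 (AR [1]) and heterogeneous autoregressive order 1 (ARH [1]) structures will be tried".

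Protocol 6.1.7 and 7.4 and SAP 4.2.4.4 withdraw a patient whose HbA1c has risen by at least 0.5% "from baseline at 2 consecutive scheduled visits which are at least 1 month apart, prior to study completion". This is one withdrawal route among several; another in Protocol 7.4 is "if the patient misses more than 10 consecutive days of study therapy".

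**The concern.** HbA1c is analysed at Weeks 4, 12, 20 and 28. Before study end the rule can trigger at Week 12 (on Weeks 4 and 12) or at Week 20 (on Weeks 12 and 20). To impute Week 20, Step 2 sees Week 12 but not Week 4. To impute Week 28, it sees Week 20 but not Weeks 4 and 12. In each case it leaves out one of the two values that caused the withdrawal.

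The regression is fitted on placebo patients who are still observed at visit t. If the rule is applied, a patient with a high value at t-1 who stays in must have had a lower value at t-2. The model learns from those patients and is applied to patients who were high at both visits.

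What is at stake is how the sensitivity analysis is read. It should differ from the primary only in what it assumes for exenatide withdrawals. If it also changes the prediction for placebo withdrawals, a gap between the two results cannot be put down to MNAR, and a sound primary result may look fragile. The HbA1c-goal sensitivity analysis in SAP 4.2.4.4 uses the same imputed data.

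**Working it through.** **The plan's own figure.** SAP 1.3 gives 122 patients at 2:1, a difference of -0.6, SD 1.0, two-sided 5% and about 87% power. SE = sqrt(3/122 + 3/244) = 0.192. Power = Φ(0.6/0.192 - 1.96) = 0.878, and 0.874 by noncentral t with 81 and 41 patients. The figure reproduces. The SAP gives no figure for the imputation.

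**Mechanism by hand.** Assume SD 1 and mean 0 at each visit and correlation 0.7 between every pair of visits. Take placebo patients whose rise at t-1 is 0.8.

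- With both lags, the prediction is 0.7/1.7 × (sum of the two values) = 0.412 × sum.
- Given 0.8 at t-1, the t-2 value has mean 0.7 × 0.8 = 0.56 and SD sqrt(1 - 0.49) = 0.714. The 0.5 threshold lies at z = (0.5 - 0.56)/0.714 = -0.084, where the density is 0.3975 and the probability below is 0.4665.
- Stayers (t-2 below 0.5) have mean t-2 value 0.56 - 0.714 × 0.3975/0.4665 = -0.05. Expected value at t: 0.412 × 0.75 = 0.31.
- Withdrawn patients (t-2 at or above 0.5) have mean t-2 value 0.56 + 0.714 × 0.3975/0.5335 = 1.09. Expected value at t: 0.412 × 1.89 = 0.78.

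A model with t-1 alone cannot tell these groups apart and is fitted on the first. A straight-line fit also uses patients with lower t-1 values, so the two figures show direction, not the exact imputed values. Under AR(1) the t-2 coefficient is zero, both groups have expectation 0.56, and nothing is lost.

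**Size by simulation.** Step 2 was simulated with 300,000 patients per arm, once with t-1 only and once with all earlier visits.

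- From the documents: visits, the two-value rule, Week 28 means 0 and -0.6, Week 28 SD 1.0.
- Assumed: visit correlations; SDs 0.7/0.9/1.0/1.0; exenatide means -0.3/-0.5/-0.6/-0.6; 3% random dropout per visit; correlation -0.3 with baseline. Everyone meeting the rule withdraws and leaves no early-discontinuation (ED) value.

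| Visit correlation | Placebo Week 28 mean: all visits / t-1 only | Effect: all visits / t-1 only | Shift |
|---|---|---|---|
| AR(1), 0.8 | 0.000 / -0.001 | -0.558 / -0.558 | 0.000 |
| Toeplitz 0.8/0.65/0.55 | -0.001 / -0.009 | -0.559 / -0.554 | 0.005 |
| Random intercept and slope | 0.001 / -0.059 | -0.568 / -0.528 | 0.040 |
| AR(1), 0.9, plus measurement error | 0.000 / -0.078 | -0.560 / -0.508 | 0.052 |
| Equal, 0.7 | -0.001 / -0.120 | -0.563 / -0.483 | 0.080 |

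The true placebo mean is 0, and using all visits recovers it in every row. The move from -0.60 to about -0.56 is the intended placebo-based penalty. Under equal correlation that penalty is 0.600 - 0.563 = 0.037, and the unplanned shift of 0.080 is about twice as large.

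**Less severe conditions.** With ED values mapped to the next visit, the shift falls to about 0.05 (equal correlation) and 0.03 (AR(1) plus error). If only half of those meeting the rule withdraw, it is about 0.03 and 0.02 without ED values, and about 0.01 to 0.03 across these structures with them.

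**At trial size.** Multiple imputation with 81 and 41 patients:

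- Equal correlation 0.7: -0.561 with all visits against -0.486 with t-1 only; significant in 79% against 71% of trials.
- AR(1) 0.8: -0.563 against -0.559; 75% against 77%, a difference within simulation error.
- No true effect, equal correlation 0.7: no bias in the difference; rejection 2.5% against 1.3%.

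**The case against.** The strongest objection is that the harm is conditional. It vanishes under AR(1) and is negligible under a near-Markov pattern, and the documents report no visit correlations. That stands. A reader might infer that the sensitivity effect is biased as a matter of fact, but the documents do not establish this.

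A reader might also infer that the placebo data are not MAR. That does not follow. MAR, as SAP 4.1.3.1 defines it, is a property of the missingness, and withdrawal on observed HbA1c values satisfies it. The fault lies in an imputation model that drops part of the observed history.

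The ED visit also weakens the effect. HbA1c is drawn there, and "the value will be programmatically mapped to the next closest scheduled visit and potentially included in the MMRM analysis". A Week 12 trigger would then fill Week 20, and a Week 20 trigger would fill Week 28, leaving less to impute. This reduces the shift without removing it. Retention is not certain either, since SAP 4.2.4.2 excludes data after discontinuation of study drug. Full enforcement is likewise an upper case, and the documents give no count of withdrawals under the rule.

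Finally, the shift is towards no effect, and SAP 4.2.4.3 wants a test that disadvantages exenatide. But the size of that disadvantage should come from the stated MNAR assumption. The SAP neither states nor justifies a first-order restriction here, and its primary model avoids one except as a convergence fallback.

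**Conclusion.** The point holds in conditional form. Step 2 gives the MAR prediction claimed for placebo only if HbA1c is first-order Markov given baseline. Otherwise placebo withdrawals under the two-value rule are imputed too low, and the placebo-based effect is attenuated: by 0 under AR(1), by about 0.01 to 0.05 in most intermediate cases, and by at most about 0.08 under equal correlation with full enforcement and no ED values. The last figure is 0.08/0.192 = 0.42 of the planning SE. These sizes assume a true effect of -0.6 with a flat placebo mean; an upward placebo drift of 0.3 raised the largest shift to 0.13. The visit correlations are assumptions throughout.

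The reach is limited. The primary MMRM is unaffected. Nothing here favours exenatide or raises the false-positive rate. A reader might suppose that the sensitivity to the supplementary analysis reuses these imputations. It does not: it includes data after rescue and after discontinuation of study drug, so it repeats the method on a different data set and needs the same correction in its own right.

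**What to change.** In SAP 4.2.4.3, Step 2, replace the single lagged covariate with HbA1c at all earlier post-baseline visits, from Week 4 up to visit t-1. These values are all available once Step 1 has made the pattern monotone. Apply the same wording to the imputation for the sensitivity to the supplementary analysis. If the sponsor prefers to keep one lag, the SAP should state the first-order restriction and justify it.

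The cost is one more parameter at Week 20 and two at Week 28. At Week 28 the model goes from 6 parameters (intercept, baseline, three for the strata, one lag) to 8. It is fitted on about 41 placebo patients less dropouts: with the roughly 30% missing in the full-enforcement runs, 41 × 0.70 is about 29. The simulations left out the strata, so sparse strata should be checked. In the AR(1) runs at trial size, where the extra terms bring nothing, the average SE rose only from 0.212 to 0.219.

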4.2.4.4 Analysis of secondary variables

Summary statistics and frequency tables will be provided for all secondary endpoints by visit and treatment for the Full analysis set during the treatment period (see Section 3.6.5 for treatment period definition), unless otherwise stated.

As for the primary analysis, data including the ED visit where applicable will be included in the MMRM/ANCOVA and CMH analysis for secondary analysis variables. Data collected from an ED visit will be mapped to the next closest scheduled visit. For patients who initiate rescue medication and continue study participation, data collected after the initiation of rescue medication will be excluded from analyses. Data collected after discontinuation of IP will be excluded from analyses for all other secondary efficacy endpoints.

Change in HbA1c from baseline Visit 3 (Week 0) to each intermediate visit

The MMRM method for change in HbA1c will be used until Week 28 and to each intermediate visit, using the Evaluable analysis set, which is the same approach as stated in Section 4.2.4.2.

The least squares mean (LSM) change from baseline and SE bar by visit will be presented in a figure by treatment group. The p-value for the difference between treatment groups by visit will also be provided in the figure.

Actual, change and percent change from baseline values of HbA1c will be summarized using descriptive statistics by visit and treatment group for the Evaluable analysis set. OC summaries will be provided.

HbA1c measures will be listed.

Proportions of patients achieving HbA1c goals

Proportions of patients having HbA1c goals of <7%, ≤6.5%, and <6.5% at Week 28 will be compared between treatments (Total EBID vs. PBO) using the Evaluable analysis set via the CMH procedure, in which screening HbA1c strata and background diabetes therapy strata will serve as the stratification factors.

A bar chart of the percentage of patients achieving HbA1c goals of <7%, ≤6.5%, and <6.5% by treatment group will be provided along with p-values.

The number and percentage of patients having HbA1c goals of <7%, ≤6.5%, and <6.5% will be summarized by visit and treatment group for the Evaluable analysis set.

Any Evaluable patient without HbA1c value at the endpoint will be considered as not achieving HbA1c goal at endpoint. The denominator will be the total number of Evaluable patients in the treatment group, and the numerator will be the number of patients achieving HbA1c <7%, ≤6.5%, and <6.5%.

As a sensitivity analysis, also in the Evaluable analysis set, the probabilities of patients reaching HbA1c targets of <7%, ≤6.5%, and <6.5% will be analyzed to Week 28 using the CMH procedure, with missing data imputed using MI pattern mixture model imputation. HbA1c and background diabetes therapy strata will serve as the stratification factors. The imputed HbA1c data for the sensitivity analysis of the primary endpoint will be used for this analysis.

Similar outputs (bar chart including p-values and summary of the numbers and percentage of patients having HbA1c goals by visit and treatment group) will be produced for the Evaluable analysis set for this sensitivity analysis.

Change in body weight, FSG and FSI from baseline Visit 3 (Week 0)

The same MMRM approach (as used for the primary analysis) will be used to analyze the change in body weight from baseline Visit 3 (Week 0) to Week 28, and each intermediate visit. Baseline body weight will replace baseline HbA1c and screening HbA1c strata will be included in these models.

Since only baseline and endpoint FSG and FSI measurements are collected, these endpoints will be analyzed by multiple imputation based on the assumption that missing data are MAR via the following steps:

Step 1: Non-monotone missing data (expected to be infrequent) will be imputed using the MCMC option of SAS PROC MI with treatment, baseline FSG/FSI, screening HbA1c strata (≤8% and >8%) and background diabetes therapy strata (drug naïve, metformin only, SU only, and metformin +SU) and value of the endpoint at each visit. This will create a monotone missing pattern in the dataset within each treatment group. This step will create 1000 imputed datasets.

Step 2: After a monotone missing pattern is created for the data, PROC MI using MONOTONE REGRESSION will be used to impute missing post-baseline values. The covariates used in the model will be treatment, baseline FSG/FSI, screening HbA1c strata (≤8% and >8%) and background diabetes therapy strata (drug naïve, metformin only, SU only, and metformin +SU) and value of the endpoint at each visit. This is MAR imputation.

Step 3: The imputed data from Step 1 and Step 2, along with observed data will be analyzed using separate ANCOVA models for each imputed dataset with change from baseline in FSG/FSI as the dependent variable and treatment, baseline FSG/FSI, screening HbA1c strata ($\leq 8\%$ and $> 8\%$) and background diabetes therapy strata (drug naïve, metformin only, SU only, and metformin +SU) as fixed effects. Parameter estimates (LS means and standard errors) and variance/covariance matrix will be obtained for each of the multiple imputed datasets.

Step 4: The estimates from multiple imputed datasets will be combined using Rubin's combination rules for statistical inference (Rubin, 1987) using PROC MI ANALYZE.

The seed used will be 88281 for both steps 1 and 2. The number of imputed datasets may be reduced depending on the extent of missing data.

The residuals from the ANCOVA model will be plotted against the quartiles from standard Normal distribution for each of the imputed datasets. A Kolmogorov–Smirnov normality test will be conducted for the residuals. If deviation from normality is noted in the ANCOVA model or imputation diagnostics including trace and autocorrelation plots indicate issues with the multiple imputation then alternative approaches will be discussed e.g. analysis of variance (ANOVA), number of imputed datasets etc.

Actual values and change from baseline will be summarized using descriptive statistics by visit and treatment group for the Full analysis set. OC summaries will be provided where appropriate.

Body weight, FSG and FSI measures will be listed.

Change in SMBG measurements from baseline Visit 3 (Week 0)

In both the seven days prior to Visit 3 (Week 0) and the seven days prior to Visit 11 (Week 28), patients will be asked to perform 4-point SMBG profiles (pre- and 2-hour post-prandial measurements at the 2 main meals of the day) on 3 separate days. SMBG profiles will be summarized as follows.

Only complete pairs of pre-prandial and post-prandial SMBG concentrations will be used. If measurements are taken for more than 2 main meals of the day, then the latest 2 meals of the day will be used that have both a pre-prandial and post-prandial measurement. If measurements were taken on more than 3 separate days in a period, then the latest 3 days of measurements that have both a pre-prandial and post-prandial measurement prior to the visit will be used. If data are missing for a meal, then the remaining available data will be used. Thus, summary measures will be calculated provided the patient had a least one complete pair of measurements in the period.

Mean SMBG will be calculated as the mean of SMBG concentrations (pre- and post-prandial) over the 2 main meals over 3 separate days, where complete pairs of both pre-prandial and post-prandial measurements for a given meal are present. Mean SMBG at baseline Visit 3 (Week 0) and Visit 11 (Week 28) as well as the change in overall daily mean from baseline Visit 3 (Week 0) to Visit 11 (Week 28) will be summarized using descriptive statistics by treatment group for the Full analysis set.

Post-prandial excursions will be calculated as the difference between the pre-prandial and post-prandial blood glucose concentrations (post-prandial – pre-prandial) and averaged (mean) over the 2 main meals over the 3 separate days in each period. Mean post-prandial excursions at

baseline Visit 3 (Week 0) and Visit 11 (Week 28) as well as the change from baseline values will be summarized using descriptive statistics by treatment group.

The mean pre-prandial (post-prandial) SMBG concentration will be defined as the average (mean) measurement over the 2 main meals over 3 separate days in each period. Mean pre-prandial (post-prandial) SMBG concentrations at baseline Visit 3 (Week 0) and Visit 11 (Week 28) as well as the change from baseline values will be summarized using descriptive statistics by treatment group.

The same multiple imputation ANCOVA approach (as used for the analysis of FSG and FSI) will be used to analyze change from baseline Visit 3 (Week 0) to Visit 11 (Week 28) for each of the 4 SMBG summary measures (overall, pre-prandial, post-prandial, post-prandial excursions).

Change in beta-cell function (HOMA-B) and insulin sensitivity (HOMA-S) from baseline Visit 3 (Week 0) to Visit 11 (Week 28)

The effects of the study medications on HOMA will be examined. The pancreatic beta-cell function (HOMA-B) and peripheral and hepatic insulin sensitivity (HOMA-S) will be computed from a computerized HOMA model, the HOMA Calculator (Matthews et al 1985). The HOMA Calculator, developed by Diabetes Trials Unit at the Oxford Center for Diabetes, Endocrinology, and Metabolism, is a computer algorithm that takes account of variations in hepatic and peripheral glucose resistance, increases in the insulin secretion curve for plasma glucose concentrations above 10 mmol/L (180 mg/dL), and the contribution of circulating proinsulin (e.g., C-peptide) to estimate the steady state beta-cell function and insulin sensitivity, as percentages of a normal reference population. The model assumes %HOMA-B and %HOMA-S values of 100% in normal young adults as a recalibration.

HOMA parameters will be log transformed (natural logarithmic transformation). The observed values and change from baseline for these parameters will be summarized by visit using descriptive statistics (n, geometric mean, geometric coefficient of variation: GCV%, geometric standard deviation factor: GSD, arithmetic mean, standard deviation, coefficient of variation: CV%, median, minimum and maximum value) for the Full analysis set.

The same multiple imputation ANCOVA approach (as used for the analysis of FSG and FSI) will be used to analyze change from baseline Visit 3 (Week 0) to Visit 11 (Week 28) for HOMA-B and HOMA-S.

All HOMA parameters will be analyzed on a logarithmic scale (natural logarithmic transformation), and then back-transformed to the original scale for result presentation using the following formulae:

$$\text{Geometric Mean} = \exp(\text{mean}(\log(X)))$$

$$\text{SE of Geometric Mean} = \text{Geometric Mean} * \text{SE of Mean}(\log(X))$$

LS means will be back-transformed in the same way.

Separate tables of back-transformed and non-transformed results will be provided.

Homeostasis results will be listed.

Proportions of patients discontinuing the study due to failure to maintain glycemic control at Visit 11 (Week 28), and at each intermediate visit

Patients should be discontinued from the study if the patient experiences a loss of glycemic control, as evidenced by:

- Increase in absolute HbA1c $\geq 0.5\%$ from baseline at 2 consecutive scheduled visits which are at least 1 month apart, prior to study completion and/or
- Fasting blood glucose >250 mg/dL (13.9 mmol/L) or non-fasting glucose >300 mg/dL (16.7 mmol/L) for 4 days in a 7-day period as measured by SMBG. The patient will return to the clinic for a confirmatory fasting glucose, if possible, or a non-fasting glucose. If by local laboratory measurement a fasting glucose is >250 mg/dL (13.9 mmol/L) or a non-fasting glucose is >300 mg/dL (16.7 mmol/L), the patient will be discontinued from the study.

A patient who discontinues because of loss of glycemic control should have discontinuation reason “Loss of Glucose Control” on their Disposition form. In addition, early patients in the study may have also discontinued due to glycemic control but only stated this on the Adverse Event form.

For the purposes of this analysis a patient will be deemed as having discontinued due to loss of glycemic control if they satisfy at least one of the following criteria:

- (a) They have discontinuation reason “Loss of glucose control” on SUM CRF form.
- (b) They have an adverse event with lower level MedDRA terms “Loss of glucose control” or “Hyperglycaemia” leading to study drug discontinuation.

The proportion of patients who discontinue the study due to failure to maintain glycemic control will be summarized using frequencies and percentages by visit for the Full analysis set. OC summaries will be provided.

A listing of patients with loss of glycemic control will be produced.

